5.3.3. Caffeine, Alcohol, and Tobacco

- Participants will abstain from caffeine -containing products for 24 hours prior to the start of dosing until collection of the final PK sample of each study period.
- Participants will abstain from alcohol for 24 hours prior (or as specified above for red wine) to admission to the CRU and continue abstaining from alcohol until collection of the final PK sample of each study period. Participants may undergo an alcohol breath test or blood alcohol test at the discretion of the investigator.
- Participants will abstain from the use of tobacco- or nicotine-containing products for 24 hours prior to dosing and during confinement in the CRU.

5.3.4. Activity

- Participants will abstain from strenuous exercise (eg, heavy lifting, weight training, calisthenics, aerobics) for at least 48 hours prior to each blood collection for clinical laboratory tests. Walking at a normal pace will be permitted.
- In order to standardize the conditions on PK sampling days, participants will be required to refrain from lying down (except when required for BP, pulse rate, and ECG measurements), eating, and drinking beverages, other than water, during the first 4 hours after dosing.
- Participants will be confined to the procedure room for the first 4 hours after dosing
 on Day 1 during continuous cardiac monitoring, except to use the bathroom. After
 this, if the equipment setup allows, participants may be ambulatory during the ECG
 monitoring period, but should not engage in strenuous activities. If equipment does
 not allow ambulation, appropriate accommodations will be made by the investigator
 site to facilitate continuous monitoring (eg, bedside urinals should be provided to
 accommodate participants' excretory needs).
- Participants will be advised to avoid direct sunlight exposure or any high intensity UV light exposure, from admission in Period 1 through the follow-up contact. In addition, participants will be instructed to apply sun cream/lotion with an SPF of ≥50, and wear eye-protective sunglasses as appropriate.

5.4. Screen Failures

Screen failures are defined as participants who consent to participate in the clinical study but are not subsequently enrolled in the study. Screen failure data are collected and remain as source and are not reported on the CRF.

Individuals who do not meet the criteria for participation in this study (screen failure) may be rescreened.

6. STUDY INTERVENTION(S) AND CONCOMITANT THERAPY

Study interventions are all prespecified investigational and noninvestigational medicinal products/auxiliary medicinal products, medical devices, and other interventions (eg, surgical and behavioral) intended to be administered to the study participants during the study conduct.

For the purposes of this protocol, study intervention refers to:

- PF-07328948;
- Placebo for PF-07328948.

6.1. Study Intervention(s) Administered

Study Intervention(s)					
Intervention Name	PF-07328948	Placebo			
Arm Name (group of participants receiving a specific treatment or no treatment)	PF-07328948	Placebo			
Type	Drug	Drug			
Dose Formulation	Bulk powder for extemporaneous preparation of oral suspensions	Bulk powder for extemporaneous preparation of oral suspensions			
Unit Dose Strength(s)	10-3000 mg	0 mg			
Dosage Level(s)	Single ascending doses 10-3000 mg	0 mg			
Route of Administration	Oral	Oral			
Use	Experimental	Placebo			
IMP or NIMP/AxMP	IMP	IMP			
Sourcing	Provided by the sponsor	Provided by the sponsor			
Packaging and Labeling	Study intervention will be provided as bulk powder for extemporaneous preparation of oral suspensions.	Study intervention will be provided as bulk powder for extemporaneous preparation of oral suspensions.			

Study Arm(s)					
Arm Title	Cohort 1	Cohort 2	Cohort 3 (Optional)		
Arm Type	Experimental	Experimental	Experimental		
Arm Description	Participants will receive up to 4 dose levels of PF-07328948 and up to 2 matching placebo. Doses will be administered as oral suspensions as escalating single doses to be determined	Participants will receive up to 4 dose levels of PF-07328948 and up to 2 matching placebo. Doses will be administered as oral suspensions as escalating single doses to be determined	Participants will receive up to 4 dose levels of PF- 07328948 and up to 2 matching placebo. Doses will be administered as oral suspensions as escalating single doses to be determined		
Associated Intervention Labels	PF-07328948; Placebo	PF-07328948; Placebo	PF-07328948; Placebo		

PF-07328948 and placebo will be provided by Pfizer as bulk powders for extemporaneous preparation of oral suspensions at the CRU.

PF-07328948 and placebo will be presented to the participants in individual dosing containers.

6.1.1. Administration

For fasted period(s):

• Following an overnight fast of at least 10 hours, participants will receive study intervention at approximately 0800 hours (plus or minus 2 hours) without breakfast on Day 1.

For period(s) when an effect of protein-rich meal (ie, MMTT) is investigated:

• Following an overnight fast of at least 10 hours, participants will be provided a protein-rich meal as 16 ounces of Ensure Plus® breakfast approximately 20 minutes prior to administration of study intervention. The entire Ensure Plus® meal is to be consumed within 10 minutes with study intervention administered approximately 10 minutes after completion of the meal at 0 hour on Day 1 (Section 5.3.2.)

For all periods, investigator site personnel will administer a single oral dose of study intervention on Day 1 of each period with ambient temperature water to a total volume of approximately 240 mL. Administer study intervention according to the EDR.

6.2. Preparation, Handling, Storage, and Accountability

1. The investigator or designee must confirm that appropriate conditions (eg, temperature) have been maintained during transit for all study interventions received and any discrepancies are reported and resolved before use of the study intervention.

- 2. Only participants enrolled in the study may receive study intervention and only authorized site staff may supply, prepare, and/or administer study intervention.
- 3. All study interventions must be stored in a secure, environmentally controlled, and monitored (manual or automated recording) area in accordance with the labeled storage conditions with access limited to the investigator and authorized site staff. At a minimum, daily minimum and maximum temperatures for all site storage locations must be documented and available upon request. Data for nonworking days must indicate the minimum and maximum temperatures since previously documented upon return to business.
- 4. Any excursions from the study intervention label storage conditions should be reported to Pfizer upon discovery along with actions taken. The site should actively pursue options for returning the study intervention to the labeled storage conditions, as soon as possible. Once an excursion is identified, the study intervention must be quarantined and not used until Pfizer provides permission to use the study intervention. Specific details regarding the excursion definition and information to report for each excursion will be provided to the site in the PCRU site procedures.
- 5. Any storage conditions stated in the SRSD will be superseded by the storage conditions stated on the label.
- 6. Study interventions should be stored in their original containers.
- 7. The investigator, institution, head of the medical institution (where applicable), or authorized site staff is responsible for study intervention accountability, reconciliation, and record maintenance (ie, receipt, reconciliation, and final disposition records), such as the IPAL or sponsor-approved equivalent. All study interventions will be accounted for using a study intervention accountability form/record.
- 8. Further guidance and information for the final disposition of unused study interventions are provided in the PCRU's site procedures. All destruction must be adequately documented. If destruction is authorized to take place at the investigator site, the investigator must ensure that the materials are destroyed in compliance with applicable environmental regulations, institutional policy, and any special instructions provided by Pfizer.

Upon identification of a product complaint, notify the sponsor within 1 business day of discovery.

6.2.1. Preparation and Dispensing

Within this protocol, preparation refers to the investigator site activities performed to make the study intervention ready for administration or dispensing to the participant by qualified staff. Dispensing is defined as the provision of study intervention, concomitant treatments, and accompanying information by qualified staff member(s) to a healthcare provider,

participant, in accordance with this protocol. Local health authority regulations or investigator site guidelines may use alternative terms for these activities.

PF-07328948 and placebo oral dosing suspensions will be prepared in the CRU by 2 operators, 1 of whom is a pharmacist. Details of dose preparation will be given in a separate EDR. Prepared doses will be provided in unit dose containers and labeled in accordance with Pfizer regulations and the investigator site's labeling requirements.

PF-07328948 and placebo will be prepared by qualified unblinded site personnel according to the EDR. Blinded study intervention will be administered in a blinded fashion to the participant.

6.3. Assignment to Study Intervention

The investigator will assign participant numbers to the participants as they are screened for the study. Pfizer will provide a randomization schedule to the investigator and, in accordance with the randomization numbers, the participant will receive the study treatment regimen assigned to the corresponding randomization number.

6.4. Blinding

This is a double-blind (sponsor-unblinded) study.

6.4.1. Blinding of Participants

Participants will be blinded to their assigned study intervention.

6.4.2. Blinding of Site Personnel

Investigators and other site staff will be blinded to participants' assigned study intervention.

Participants will be assigned to receive study intervention according to the assigned treatment group from the randomization scheme. Investigators will remain blinded to each participant's assigned study intervention throughout the course of the study.

In order to maintain this blind, an otherwise uninvolved third party will be responsible for the preparation and dispensing of all study intervention and will endeavor to ensure that there are no differences in time taken to dispense or visual presentation, following randomization or dispensing.

In the event of a Quality Assurance audit, the auditor(s) will be allowed access to unblinded study intervention records at the site(s) to verify that randomization/dispensing has been done accurately.

PCRU Pharmacy staff responsible for preparing all study intervention will be unblinded. PCRU site staff providing technical system support to the Pharmacy staff, and supporting blinded laboratory data processes will be unblinded. These site staff providing system support are not involved in any data collection or clinic floor activities.

6.4.3. Blinding of the Sponsor

As this is a sponsor-open study, a limited number of the sponsor's team members (excluding site staff) may conduct unblinded reviews of the data during the course of the study for the purpose of safety and tolerability assessment, facilitating doseescalation decisions, facilitating PK/PD modeling, and/or supporting clinical development. Unblinded results will be reviewed by a designated limited number of sponsor colleagues within the study team.

6.4.4. Breaking the Blind

The method for breaking the blind in this study will be manual. In case of an emergency, the investigator has the sole responsibility for determining if unblinding of a participant's treatment assignment is warranted. Participant safety must always be the first consideration in making such a determination. If the investigator decides that unblinding is warranted, the investigator should make every effort to contact the study medical monitor prior to unblinding a participant's treatment assignment unless this could delay further management of the participant. If a participant's treatment assignment is unblinded, the sponsor must be notified within 24 hours after breaking the blind. When the blinding code is broken, the reason must be fully documented in a CRF.

Blood specimens will be obtained from all participants for PK analysis to maintain the study blind at the investigator site. Only the investigator site staff will be blinded to study treatment. Other Pfizer personnel will be unblinded to participant treatments in order to permit real-time interpretation of the safety and PK data; and provide information necessary to potentially alter the dose-escalation sequence. The blinded study monitor, if assigned, will remain blinded to treatment until all monitoring for the study has been completed. Specimens from participants randomized to placebo will not be routinely analyzed. To minimize the potential for bias, treatment randomization information will be kept confidential by Pfizer unblinded personnel and will not be released to the blinded investigator or blinded investigator site personnel until the study database has been locked or the investigator requests unblinding for safety reasons.

6.5. Study Intervention Compliance

When the individual dose for a participant is prepared from a bulk supply, the preparation of the dose will be confirmed by a second qualified member of the study site staff.

When participants are dosed at the site, they will receive study intervention directly from the investigator or designee, under medical supervision. The date and time of each dose administered in the clinic will be recorded in the source documents and recorded in the CRF. Study site personnel will examine each participant's mouth to ensure that the study intervention was ingested.

6.6. Dose Modification

The decision to proceed to the next dose level of PF-07328948 (either an increase or a decrease) will be made by the study team and the investigator based on safety, tolerability, and preliminary PK data obtained in at least 6 participants (including at least 1 placebo

participant) at the prior dose level. Safety data and PK data through at least 48 hours and 24 hours post-dose, respectively, will be reviewed.

The dosing schedule may also be adjusted to expand a dosing cohort to further evaluate safety, tolerability, PK, and/or PD findings at a given dose level or to add cohorts to evaluate additional dose levels or repeat dose levels. The study procedures for these additional participant(s)/cohort(s) will be the same as that described for other study participants/cohorts.

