Days Relative to Day 1	Day -28 to Day -3	Day -2	Day -1	Day 1		ay 2	Day 3	Day 4	Visit: Day 8±1	Contact: 28-35 days		All screening should be done ≤28 days before the first dose. Day relative to start of study intervention (Day 1). Day 1 activities at time=0 hour are prior to the dose, except				
Hours After Dose				0	24	24 36		72		v		for study intervention administration. On-site follow-up visit occurs on Day 8±1 after administration of the final dose of study intervention. Follow-up may occur via telephone contact and must occur 28 to 35 days after administration of the final dose of study intervention.				
Contraception check	X	X	X					X	X	X	X	Contraception only required for male study participants. Contraceptive guidance is outlined in Appendix 4. If performed on Day -2 at admission, assessment is not needed on Day -1				
COVID-19 related measures		X	X	X	X		X	X	X		X	Per CRU procedures.				
CRU discharge					XX			X				Participants may be asked to remain at the CRU after completion of Day 4 activities at the discretion of the investigator or if safety, tolerability, or PK data dictate the need to prolong inpatient stay at the CRU				
Serious and nonserious AE monitoring	X	\rightarrow	\rightarrow	\rightarrow	\rightarrow	\rightarrow	\rightarrow	\rightarrow	\rightarrow	X	X	See Section 8.4.3 for follow-up AE and SAE assessments.				
Physical exam	X	X		able 2				X	X		X	Complete PE at Screening or upon admission for a participant's first period in the study; at all other time points, brief PE performed for findings during previous exam or new/open AEs, at investigator discretion. Including height and weight only at screening See Section 8.3.1 for additional information.				
Neurological examination				See Table	X				X		X	Complete neurological exam for timepoints on Day 1 (see Table 2) and 24 hours after dosing on Day 1. At other time points, neurological exam at investigator discretion. See Section 8.3.2 for additional information.				
Respiratory rate					X		X	X	X		X	Single assessment at all timepoints See Section 8.3.3 for additional details.				

 Table 1.
 Study Schedule of Assessment

Visit Identifier Abbreviations used in this table may be found in Appendix 10.	Screen]	Period 1 In-	l to F -patio		14		Foll	ow-Up	ET	Notes				
Days Relative to Day 1	Day -28 to Day -3	Day -2	Day -1	Day 1		ay 2	Day 3	Day 4	Visit: Day	Contact: 28-35		All screening should be done ≤28 days before the first dose. Day relative to start of study intervention (Day 1).				

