Safety laboratory tests	X	X	X		X			X	X		X	Participant should fast for at least 4 hours prior to sample collection. If performed on Day-2 at admission, safety lab tests are not needed on Day -1. Results of any pre-dose safety labs should be reviewed and confirmed acceptable prior to dosing.				
Retained Research Sample for Genetics (Prep D1.5)				X								Collected in first period only. If not collected on the designated collection day, collect at the next available time point when biospecimens are being collected in conjunction with a participant visit. See Section 8.6.2 for additional details.				
Pfizer Prep B1.5 retained research sample				X	X							Samples to be collected as outlined in Section 8.7.1.4. Samples will be collected in Period 1 and Period 4 only for				
Pfizer Prep B2.5 retained research sample				X	X							each cohort				
HIV, HBsAg, HBsAb, HBcAb, HCVAb	X											See Appendix 2: Clinical Laboratory Tests.				
FSH	X											Only for females who have been amenorrheic for at least 12 months.				
Urine samples for:																
Urine drug testing	X	X	X									If performed on Day-2 at admission, urine drug testing is not needed on Day -1. Results of any pre-dose testing should be reviewed and confirmed acceptable prior to dosing. See Appendix 2: Clinical Laboratory Tests				

 Table 1.
 Study Schedule of Assessment

Visit Identifier Abbreviations used in this table may be found in Appendix 10.	Screen]	Period 1 In-	l to P patie		14		Foll	ow-Up	ET	Notes					
Days Relative to Day 1	Day -28 to	Day		Day	D	ay	Day	Day		Contact:		All screening should be done ≤28 days before the first dose.					
	Day -3	-2	-1	1	4	2	3	4	Day 8±1	28-35 days		Day relative to start of study intervention (Day 1). Day 1 activities at time=0 hour are prior to the dose, except					
Hours After Dose				0	24	36	48	72	U-1	unys		for study intervention administration. On-site follow-up visit occurs on Day 8±1 after administration of the final dose of study intervention. Follow-up may occur via telephone contact and must occur 28 to 35 days after administration of the final dose of study intervention.					
Urinalysis (with microscopy, if needed)	X	X	X		X			X	X			Participant should fast for at least 4 hours prior to sample collection. If performed on Day-2 at admission, urinalysis not needed on Day -1. Results of any pre-dose testing should be reviewed and confirmed acceptable prior to dosing. See Appendix 2: Clinical Laboratory Tests					

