Participants confirming eligibility according to Section 5 will be admitted to the CRU on Day -2 in Period 1 for each cohort and the 1st food period (if applicable) within a cohort. For all other periods (ie, Periods 2-4 except the 1st food period within each cohort), participants will be re-admitted to the CRU on Day -1. For each period in this study, on Day 1, following ≥10-hour overnight fast, participants will receive a single oral dose of PF-07328948 or placebo. Participants have been discharged on Day 3 in Cohort 1 and will be discharged on Day 4, following completion of all scheduled assessments out to 72 hours post-dose in Cohort 2 and optional Cohort 3. Participants may stay in the CRU after completion of Day 4 activities at the discretion of the investigator. In each cohort, a washout interval of at least 7 days will be introduced between subsequent doses. During the washout interval, emerging 24-hour PK and 48-hour safety data will be reviewed and the next dose will be determined. An on-site follow-up visit on Day 8±1 after the final dose and a final follow-up within 28-35 days after the final dose will be scheduled. Final follow-up may be a phone contact or an on-site visit at the discretion of the PI.

Based on the review of emerging safety, tolerability, and PK data (and PD data if available) in Cohorts 1 and 2, the optional third cohort may enroll 8 participants (crossover, placebo-controlled design) to explore additional doses, to repeat a dose, to evaluate split dosing, or to investigate food effects on PK and PD biomarkers.

Dosing will occur in the fasted state for all periods for dose escalation. The effect of a high-protein meal on safety, tolerability, PK exposure, and PD biomarkers may be assessed in at least 1 period within Cohort 2 and/or Cohort 3.

Participants should only need to undergo these time-matched assessments of PD biomarkers on Day -1 once in the fasted state and/or once in the fed state in each cohort, unless there is any uncertainty regarding the reliability of the initial Day -1 assessment. In addition, if thought necessary to achieve study objectives, study intervention may be administered in the fed state (eg, following a high-protein meal) during any of the study periods/cohorts.

The total duration of participation from the screening visit to the telephone follow-up contact will be approximately 14 weeks.

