Lunch and dinner will be standardized when participants are confined in the CRU; additional efforts will be made to ensure lunch, dinner and snacks are as identical as is feasible on Day 1 for each period and on Day -1 where time-matched assessment is performed (Section 5.3.2).

CCI

Based on predicted half-life in human (~4 hours), PK samples were collected over 48 hours post-dose in Cohort 1. However, the preliminary PK data emerging from Cohort 1 suggested the terminal half-life could be longer than the predicted 4 hours therefore, participants in remaining Cohort 2 and optional Cohort 3 will be confined in CRU up to Day 4 with PK samples collected up to 72 hours post-dose. A washout interval of ≥ 7 days is proposed between doses within an individual participant; this interval should be sufficient based on all emergent PK data to date, and the projections that CCI levels return to baseline within approximately 72 hours post-dose based on a PK/PD model developed with preclinical data and emergent PK/PD data in Cohort 1. In addition, this washout interval should offer sufficient opportunity to review safety, tolerability, and PK data after each dosing period prior required for decision on the PF-07328948 dose to be evaluated in the subsequent period. However, sampling times, duration of sampling, and/or the length of the washout period may be modified and/or extended based on emerging PK and/or PD data. Participants may be asked to remain at the CRU after completion of Day 4 activities at the discretion of the investigator or if safety, tolerability, or PK data dictate the need to prolong inpatient stay in the CRU. The planned doses and assignment to study intervention in the escalation sequence (see Section 1.2) may be modified or repeated, as guided by emerging safety, tolerability, and PK data but will follow the dose-escalation rules defined in Section 6.6.1.

Decreased blood pressure was observed after single doses (≥ 20 mg/kg) of PF-07328948 in dogs in exploratory toxicology studies; however, no significant blood pressure changes were subsequently noted in GLP toxicology studies after single doses of ≤ 100 mg/kg in dogs. Serial triplicate assessment of blood pressure will be performed following single dose administration as outlined in SoA. Triplicate 12-lead ECGs and continuous cardiac telemetry

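### Does the 48-hour safety review before the next dose leave out the 72-hour laboratory panel in Cohorts 2 and 3?

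*Protocol*

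**What the plan says.** Two protocol sections set the safety data needed for the next-dose decision. Section 6.6 states: "Safety data and PK data through at least 48 hours and 24 hours post-dose, respectively, will be reviewed". Section 4.1, describing the washout, says that "emerging 24-hour PK and 48-hour safety data will be reviewed and the next dose will be determined". Section 6.6 words 48 h as a minimum; Section 4.1 simply names it.

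Table 1 in Section 1.3 fixes when the data are collected. Safety laboratory tests and urinalysis have in-period post-dose marks at 24 h and 72 h, and their 36 h and 48 h cells are empty. Supine blood pressure and pulse rate, respiratory rate and 12-lead ECG are marked at 24, 48 and 72 h. The Day 8±1 visit follows the final dose only. The Day 4 physical examination is discretionary ("at all other time points, brief PE performed for findings during previous exam or new/open AEs, at investigator discretion"), so it has no bearing here.

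Other text that bears on the decision:

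- Section 4.1: "In each cohort, a washout interval of at least 7 days will be introduced between subsequent doses". Section 4.2 says that the washout "is proposed between doses within an individual participant".
- Table 1, safety laboratory row: "Results of any pre-dose safety labs should be reviewed and confirmed acceptable prior to dosing".
- Section 6.6.1 allows progression only if the last dose level was well tolerated and the available safety and PK data have been satisfactorily reviewed. One of its stopping criteria concerns clinically significant laboratory abnormalities in at least half of the participants on active drug at a dose level.
- Section 6.6 also allows the sponsor to "add cohorts to evaluate additional dose levels or repeat dose levels".

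**The concern.** The two parts of the protocol seem to have come apart. The summary of changes for the current amendment says that laboratory tests and urinalysis moved from Day 3 to Day 4 when the stay was lengthened to 72 h for Cohort 2 and optional Cohort 3. A review through 48 h would have reached a Day 3 panel. It does not reach a Day 4 panel, and the figure in Sections 4.1 and 6.6 is still 48 h.

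If 48 h were applied as the whole requirement, the next dose level could be chosen on one post-dose laboratory panel and one urinalysis per participant. An abnormality first visible at 72 h could then be missed at the decision. This would matter because laboratory findings are an explicit stopping criterion. Section 4.2 also says that the half-life looked longer than the predicted 4 h, which makes later sampling more informative.

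**Working it through.** **Inputs.** Review minimum of 48 h (Sections 4.1 and 6.6). Assessment times from Table 1. Washout of at least 7 days (Section 4.1). At least 24 h of sentinel data before the remaining participants are dosed (Section 6.6.1). Admission on Day -2 for Period 1 of each cohort and for a cohort's first food period, otherwise Day -1 (Section 4.1).

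**1. Panels reached by the floor alone.** In-period post-dose assessments in the Table 1 columns from 24 h onward, per participant and period:

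| Assessment | Times (h) | By 48 h | By 72 h |
|---|---|---|---|
| Safety laboratory tests | 24, 72 | 1 | 2 |
| Urinalysis | 24, 72 | 1 | 2 |
| Blood pressure and pulse | 24, 48, 72 | 2 | 3 |
| Respiratory rate | 24, 48, 72 | 2 | 3 |
| ECG | 24, 48, 72 | 2 | 3 |

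The floor reaches 1 of 2 laboratory panels. After a cohort's final dose it reaches 1 of 3 (24 h, 72 h, Day 8±1). The count behind the concern is correct.

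**2. When the 72 h panel exists, within a cohort.** The washout is 7 × 24 = 168 h.

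- Same participant: 168 − 72 = 96 h from the 72 h draw to that participant's next dose, at least.
- Whole cohort: let the last participants be dosed s hours after the sentinels. The earliest next-period dose is 168 h after the sentinel dose, so the last 72 h draw precedes it by 168 − (s + 72) = 96 − s hours.
 - s = 24 (the shortest stagger): 72 h.
 - s = 48 (assumed): 48 h.

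**3. The panel after that.** Before Periods 2 to 4, laboratory tests and urinalysis are repeated on Day -1, or on Day -2 before a cohort's first food period. With the shortest washout these fall about 168 − 24 = 144 h or 168 − 48 = 120 h after the participant's previous dose. Both are later than 72 h, and the results are to be reviewed before dosing. Within a cohort, these are the participants who took the previous dose level, apart from any replacements.

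**4. What the text requires once results exist.** A 72 h result that has been reported is available safety data, so the Section 6.6.1 progression condition covers it. It also counts toward the laboratory stopping criterion, which has no cut-off time. Section 8.3.5 requires the investigator to review each laboratory report and document that review. Section 9.3.1 has safety laboratory data reviewed on an ongoing basis.

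**5. A step to new participants.** The washout and the pre-dose check both attach to the individual, so neither covers the first period of a new cohort, and no minimum interval between cohorts is stated. Period 1 does require admission about 48 h before dosing. If admission follows the 48 h review (an assumption; the protocol does not say so), the first new dose comes about 48 + 48 = 96 h after the dose under review, which is 24 h after its 72 h draw.

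**The case for a change.** The best argument for a change is that none of these safeguards names the 72 h results as a required input. Available data are whatever has arrived. The pre-dose check decides whether one person may be dosed, not whether the dose level is acceptable. New participants in optional Cohort 3 or an added cohort have neither the washout nor prior exposure to rely on. Section 2.3.1 counts serial liver function tests and blood counts among the mitigations for idiosyncratic reactions, and the minimum alone secures only one post-dose panel. In a first-in-human escalation one would prefer a written requirement to reliance on practice, and it would cost about one sentence in each of two sections.

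Part of this stands. The floor alone reaches only the 24 h panel, Sections 4.1 and 6.6 are worded differently, and the interval between cohorts is not fixed.

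The rest does not make it a defect. A minimum of 48 h and a panel at 72 h are compatible, so no passages conflict. Vital signs and ECG are measured at 48 h and adverse events are followed throughout, so the 48 h review has real content. Nothing in the protocol says that two laboratory panels are needed for each decision. Optional Cohort 3 opens only after review of emerging data from Cohorts 1 and 2, and it may repeat a dose, split it or test food rather than escalate. Any escalating period also begins with sentinels, one on active drug and one on placebo, and a review through at least 24 h.

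**Conclusion.** The concern does not call for a change. It identifies a detail left unwritten, which a study team following the protocol fills sensibly. By the 48 h minimum alone, 1 of 2 in-period laboratory panels and 1 of 2 urinalyses are assured in Cohorts 2 and 3. Within a cohort, the 72 h samples are drawn 48 to 72 h before the earliest next dose, the progression rule covers them once reported, and a later panel is reviewed before dosing. No endpoint, analysis or stopping criterion is altered.

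This rests on three assumptions: a sentinel stagger of 24 to 48 h, laboratory results returned within the 48 to 72 h that remain (the documents give no turnaround time), and the column reading of Table 1, which agrees with the summary of changes.

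The residue is a step to new participants with no stated minimum interval. It is narrow, depends on an optional or hypothetical cohort, and has not been shown to lead to a missed finding. The sponsor may align the wording of Sections 4.1 and 6.6 with Table 1 if the protocol is being amended for other reasons. Which time points the decision should rest on is for the sponsor and the investigator.
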